## **STUDY PURPOSE AND RATIONALE**

Translating good clinical practice and best evidence into the care and management of central lines poses many challenges. Several experts have identified the existing gap between

policy awareness and adherence among providers and clinicians. A comprehensive review of the literature from 2001 to 2015 found few studies describing and quantifying existing clinician variability in care and management of centrally and peripherally inserted catheters. Therapeutic interventions in 21st century healthcare is assumed to be based on evidence demonstrating a net beneficial effect that is without supporting data. CMS value based purchasing now demands stakeholders (i.e. purchasers, payers, providers, clinicians, patients, and policy makers) to change the measurement of healthcare quality from the historical practice of individual judgement based primarily on clinician credentials to metrics. The high prevalence of central lines mandates a paradigm shift from the standard perception of complications being “inevitable” to “unacceptable” thereby setting elimination as the goal versus the current benchmarking comparisons. Specific outcome metrics for central lines should be identified in individual organizations with specific performance metrics. Hospitals need to monitor clinician adherence to specified outcome metrics for CVCs, PICCs and HD catheters.

The aim of this study is to document clinicians variation in practice in comparison to standard guidelines by the Medical Center’s approved Evidence-based Practice (EBP) guidelines, policies, and procedures for CVCs, PICCs and HD catheters by way of a structured retrospective review of the EMR system. This study will assist in future translational research and to design a prospective study on CVCs, PICCs and HD catheters.

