## **INCLUSION CRITERIA**

Adult patients in MICU, CCU, CSICU, SICU and hemodialysis with either CVCs, PICCs, or HD catheters.

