## **EXCLUSION CRITERIA**

Pediatric (including neonates), obstetric and gynecology, medical-surgical, and oncology patients.

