
## Appendix C

### CASCADE STUDY DATA COLLECTION TOOL

| Please provide in this format: |            |             |     | Not in this format: |            |                          |     |
|--------------------------------|------------|-------------|-----|---------------------|------------|--------------------------|-----|
| MRN                            | HAR        | Medication  | ... | MRN                 | HAR        | Medication               | ... |
| 1234567                        | 2000000001 | Albuterol   | ... | 1234567             | 2000000001 | Albuterol
Simvastatin | ..  |
| 1234567                        | 2000000001 | Simvastatin | ... |                     |            |                          |     |

| Item  | Values/examples   | Description  |
|---|---|--|
| MRN   | 7 or 9 digit number   | Patient's MRN  |
| HAR   | 10 digit number   | Patient's HAR  |
| Name  | XXX, XXX alphanumeric   | Patient full name  |
| Sex   | Male/Female   | Patient's gender   |
| Age   | Number  | Patient's age at admission (number)  |
| Line, Drain, Airway, Tubes and Wound (LDAW) of the following types: CVC, PICC and PIV             | Include only the following: CVC Double Lumen, CVC Single Lumen, Peripheral IV, PICC Double Lumen, PICC single lumen, PICC Triple Lumen                                  | Specifies the type of LDAW that was placed   |
| Date of LDAW placement  | XX/XX/XXXX X:XX:XX AM/PM  | The date and time the LDAW was placed  |
| Date of LDAW removal  | XX/XX/XXXX X:XX:XX AM/PM  | The date and time the LDAW was removed   |
| Calculated field:
Duration of LDAW  | Number of hours   | This can be calculated by subtracting the LDAW placement date from the LDAW removal date. Please present results to hours.   |
| LDAW Removal Reason   | Discharge, Catheter damage, therapy complete, leaking, occluded, per order, per protocol, purulent drainage, removed by patient, infiltrated, phlebitis, site change, other (comment) | The reason that the LDAW was removed   |
| Calculated field:
Unit in which the LDAW was placed                                     | Any hospital unit name  | This unit can be determined based on the following criteria: the time of LDAW placement falls between admission into this unit AND before transferred out of or is discharged from this unit.  |

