| Calculated field:
Unit in which the LDAW was removed                                    | Any hospital unit name  | This unit can be determined based on the following criteria: the time of LDAW removal falls between admission into this unit AND before the patient is transferred out of or is discharged from this unit  |
| Calculated field:
Was Cathflo (alteplase) administered during the duration of the LDAW? | Yes, No   | This can be determined based on the following criteria:
Yes if the time that during which Cathflo was administered falls within the timeframe that an LDAW was in place (i.e. after it was placed, but before it was removed)
No if the time that during which Cathflo was administered does not fall within the timeframe that an LDAW was in place (i.e. after it was placed, but before it was removed) |

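### Appendix C tells the extractor to collect peripheral IVs, which lie outside the study's stated scope, and the plan gives no purpose or filter for those rows

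*Combined protocol and SAP*

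**What the plan says.** The study's scope is stated consistently. Study Purpose and Rationale sets the aim against hospital "policies, and procedures for CVCs, PICCs and HD catheters by way of a structured retrospective review of the EMR system". Inclusion Criteria admits "Adult patients in MICU, CCU, CSICU, SICU and hemodialysis with either CVCs, PICCs, or HD catheters". The research questions, hypothesis, objectives and endpoints name the same three catheter types, and Sample Size plans 175 CVCs, 75 PICCs and 50 HD catheters. Peripheral IVs appear in none of these sections.

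The extraction tool differs. Data Collection Tool refers to Appendix C for the items, values and descriptions. There the line item is labelled "Line, Drain, Airway, Tubes and Wound (LDAW) of the following types: CVC, PICC and PIV", where LDAW is the record system's category for lines and devices. Its value column restricts the extract to "CVC Double Lumen, CVC Single Lumen, Peripheral IV, PICC Double Lumen, PICC single lumen, PICC Triple Lumen".

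The fields that follow are defined per LDAW with no restriction to central lines:

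- Duration: "This can be calculated by subtracting the LDAW placement date from the LDAW removal date".
- Removal reason: "The reason that the LDAW was removed", with values that include infiltrated, phlebitis and site change.
- Unit of placement and unit of removal.
- Cathflo (alteplase) given: Yes if the administration time "falls within the timeframe that an LDAW was in place".

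Exclusion Criteria lists patient types only: "Pediatric (including neonates), obstetric and gynecology, medical-surgical, and oncology patients". Data Analysis and Data Management mention no selection by line type.

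**The concern.** An extraction instruction is operative text: whoever runs the query will follow it. Followed as written, it returns peripheral IVs alongside the central lines in the same fields. If the rows were then summarised together, three things could go wrong.

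- Line counts and dwell would describe a mixture of central and peripheral lines while being reported as results for CVCs, PICCs and HD catheters.
- Removals for infiltration or phlebitis of a peripheral line could be tallied with central-line removals.
- The Cathflo flag would pick up false positives from peripheral lines that happened to be in place at the time.

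There is also no standard by which to judge a peripheral row. The primary endpoint splits management into adherent and non-adherent with hospital guidelines, and the guidelines chosen do not include one for peripheral IVs.

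**Working it through.** The plan states no figure on this point, so the check is mainly a comparison of sections.

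1. **Scope against list.** The Appendix C list has six types: two CVC, three PICC and one peripheral IV. Five fall within scope and one does not. The planned sample is 175 + 75 + 50 = 300, which is complete with no peripheral IVs.

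2. **Is it a slip in reading the table?** No. The abbreviation PIV stands in the item label and the full term stands in the value list, so the entry was written twice.

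3. **Does another section remove the rows?** No. The exclusions act on patients, so a peripheral IV in an eligible patient passes through them. Data Analysis and Data Management contain no line-type restriction and no peripheral comparison group.

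4. **Is there an adherence standard?** The eight policies under Methodology cover apheresis catheters, central venous catheters, adult dialysis catheters, implanted devices, PICCs, dialysis through a central catheter, central cannulas, and central catheters for parenteral nutrition. The short peripheral policy (I-3) appears in Appendix A only as a cross-reference.

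5. **Cathflo rule.** Suppose a patient has a PICC and a peripheral IV in place together and the PICC is treated. The administration time lies inside both placement intervals, so the written rule codes Yes on both rows. This follows from the rule and needs no assumption beyond overlapping lines.

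6. **Related gap.** The same list has no HD catheter entry and no CVC triple lumen entry, although 50 HD records are planned and Appendix B carries a triple-lumen form. That is a separate omission, but the same edit should deal with it.

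**Illustration of size.** Every input here is an assumption, because the documents give no peripheral IV count and no dwell data. Let k be the number of peripheral IVs per central line.

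- Share of rows that are peripheral = k/(k + 1). For k = 0.5, 1, 2 and 3 this is 33%, 50%, 67% and 75%.
- Suppose dwell is exponential with mean 8 days (central) and 3 days (peripheral), and all rows are pooled. The median m solves [exp(−m/8) + k·exp(−m/3)]/(1 + k) = 0.5. With k = 0, m = 8 × ln 2 = 5.5 days. For k = 0.5, 1, 2 and 3, m = 3.9, 3.3, 2.8 and 2.6 days.
- At k = 1, a peripheral mean of 2 days in place of 3 gives 2.6 days. A central mean of 6 days moves the median from 4.2 to 2.9, and a central mean of 12 days moves it from 8.3 to 3.9.

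The direction is the same throughout, and the size depends wholly on the inputs.

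**The case against.** The strongest reply is that collecting rows is not the same as analysing them. Appendix C records the type of each line, so peripheral rows are labelled and one filter removes them. No section says that types will be pooled, and an analysis faithful to the objectives and the sample would leave them out. This stands. A reader might infer that dwell will be understated or that central-line results will be diluted, but the documents do not support that as a certainty.

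Several further limits also stand.

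- Eligibility is set by patient. The list does not admit ineligible patients; it admits out-of-scope lines in eligible ones.
- The headings for catheter dwell and for complications point to Appendix B, whose legible part is a CVC form. Appendix C is not shown to be the only source for dwell, and no path is shown from its line list to the complication counts.
- Removal reason and Cathflo are not named among the primary or secondary endpoints.
- No section says that infiltration, phlebitis or site change apply to peripheral lines alone.
- A single 8-day mean fits poorly with the Background section, which describes use ranging from days to years by catheter type.

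Finally, the entry may be deliberate. Appendix C also collects irritant and vesicant IV drugs, for which peripheral access could be useful context. No section says so, however. What the reply does not answer is the absence of any stated purpose or filter, or the Cathflo rule, which miscodes peripheral rows as written.

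**Conclusion.** The inconsistency is real. Appendix C instructs extraction of a line type that the aim, objectives, endpoints, inclusion criteria, sample and adherence policies do not cover, and the plan neither explains nor filters it. The consequence is a risk that out-of-scope lines enter line-level dwell, removal-reason and Cathflo summaries. It is not a demonstrated bias in a planned result, because the rows are labelled and pooling is not prescribed.

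The size cannot be determined from the documents. The illustrative shares (33% to 75% of rows) and medians (5.5 days falling to between 3.9 and 2.6 days for 0.5 to 3 peripheral IVs per central line) rest on assumed line counts, assumed exponential dwell and complete pooling. They should not be cited as estimates for this study. The point still merits correction, because it concerns an operative instruction and costs almost nothing to put right before extraction.

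**What to change.** Reconcile the Appendix C line list with the study's scope by deleting PIV from the item label and Peripheral IV from the value list. In the same edit, check the list against the eligible catheter types, since it has no HD catheter or CVC triple lumen entry.

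If peripheral IVs are wanted as context for IV drug route, state that purpose, hold them in a separate table, and add a sentence to Data Analysis that restricts all line counts and all dwell, removal-reason and Cathflo summaries to CVC, PICC and HD catheter rows. Where the record allows it, link the Cathflo flag to the line treated and not to any line in place at the time.

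The cost is one edit to the extraction request and, for the second option, one sentence in the analysis section. No additional records need be reviewed on account of the peripheral entries.

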#### **Thrombotic Complication**

- Thrombotic occlusion
- Catheter patency rate
- Drug precipitates

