## Appendix C

**The following information will be acquired from Omnicell**

| Item  | Values/examples  | Description   |
|---|--|---|
| MRN   | 7 or 9 digit number  | Patient's MRN   |
| HAR   | 10 digit number  | Patient's HAR   |
| Completed administrations of Irritant/Vesicant Intravenous Medication | 
Name of IV Medication the patient was ordered:
 
 
• Acyclovir
 
• Amphotericin B
 
• Ampicillin sodium
 
• Ampicillin sodium/sulbactam sodium Partial parenteral nutrition
 
• Chemotherapeutic agents
 
• Ciprofloxacin
 
• Dextrose 10% or greater
 
• Dopamine
 
• Erythromycin
 
• Fluconazole
 
• Ganciclovir sodium
 
• High-concentration potassium chloride
 
• Iron dextran
 
• Mannitol
 
• Meperidine hydrochloride
 
• Morphine sulfate
 
• Nafcillin sodium
 
• Norepinephrine
 
• Oxacillin sodium
 
• Phenytoin sodium
 
• Promethazine hydrochloride
 
• Sodium bicarbonate
 
• Sodium nitroprusside
 
• Ticarcillin disodium
 
• Tobramycin sulfate
 
• Total parenteral nutrition (TPN)
 
• Vancomycin
 
 | A list of all irritant/vesicant medications that the patient was administered via intravenous route |

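### Appendix C returns Cathflo use as Yes/No without dose times, so catheter patency can be estimated only crudely and not by a standard time-to-event method

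*Combined protocol and SAP*

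**What the plan says.** The Secondary Endpoints section lists "Catheter patency rate" under Thrombotic Complication, with no numerator, denominator or time point.

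The data collection tool in Appendix C asks, per line, "Was Cathflo (alteplase) administered during the duration of the LDAW". The permitted values are Yes and No, and the rule for Yes is "Yes if the time that during which Cathflo was administered falls within the timeframe that an LDAW was in place". Around that field the tool asks for:

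- placement: "The date and time the LDAW was placed";
- removal: "The date and time the LDAW was removed";
- dwell in hours: "This can be calculated by subtracting the LDAW placement date from the LDAW removal date";
- a removal reason, whose values begin "Discharge, Catheter damage, therapy complete, leaking, occluded, per order, per protocol".

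The Omnicell part of Appendix C is described as "A list of all irritant/vesicant medications that the patient was administered via intravenous route". Alteplase is not among the drugs named there, and no administration time is requested.

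The Data Analysis section plans correlation, two-group and multi-group comparisons, and Fisher or chi-square tests. It contains no time-to-event method.

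**The concern.** Patency is a property of a line over time: it works until some moment and then does not. To fill in the Cathflo field, the query must compare each administration time with placement and removal. What comes back merges a first dose on day 1 with one on day 60, and one dose with five. The start and end of dwell are kept, but the moment at which function was first lost is missing for any line that was treated and stayed in.

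This matters because the catheters being compared differ in intended dwell. The Background section describes non-tunneled lines for days to weeks, PICCs for weeks to months and tunneled CVCs for months to years. An ever/never flag rises with time in place. A plain proportion compared between catheter types or adherence groups by a chi-square or Fisher test therefore mixes differences in patency with differences in dwell.

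**Working it through.** The documents state no patency rate or time to occlusion, so there is no planned figure to reproduce. The check asks which patency measures the extract determines.

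**Items available per line (Appendix C):** placement time, removal time, dwell hours, Cathflo Yes/No, and removal reason including 'occluded'.

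**Set-up.** 300 lines (the planned number of records). Assumed: Cathflo-Yes share of 14%, 25% or 36%; dwell of 0.5 day plus an exponential time with mean 7 or 14 days; no removals for occlusion. The extract was held fixed, and only the unrecorded first-dose time was moved, to 2%, 50% or 98% of each line's dwell.

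**Measures that the extract fixes**

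- Crude patency = (lines − Yes lines) / lines. At 36%: (300 − 108)/300 = 0.64. At 25%: (300 − 75)/300 = 0.75. At 14%: (300 − 42)/300 = 0.86. Dose times do not alter these.
- Yes lines per 1000 total dwell-days. At 36%: 44.9 (exponential mean 7) and 28.0 (mean 14).

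**Measures that the extract does not fix**

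| Yes share, exponential mean | First dose at | Day-7 Kaplan-Meier patency | Events per 1000 patent days | Median days to first Cathflo |
|---|---|---|---|---|
| 36%, 14 d | 2% of dwell | 0.639 | 46.4 | 0.22 |
| 36%, 14 d | 50% | 0.757 | 35.1 | 5.38 |
| 36%, 14 d | 98% | 0.844 | 28.2 | 10.55 |
| 14%, 14 d | 2% | 0.860 | 11.9 | 0.24 |
| 14%, 14 d | 98% | 0.951 | 10.2 | 11.88 |
| 36%, 7 d | 2% | 0.639 | 72.1 | 0.14 |
| 36%, 7 d | 50% | 0.610 | 55.6 | 3.41 |
| 36%, 7 d | 98% | 0.734 | 45.3 | 6.69 |

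In the first scenario the total-dwell rate of 28.0 could stand for a patent-day rate of up to 46.4. It would then be too low by 1 − 28.0/46.4 = 40%.

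**How far the inputs can be trusted.** The 14% to 36% range is borrowed from the Background section, where it refers to occlusion within one to two years, not within a stay of a week or two. Read at a constant hazard, it implies −ln(1 − 0.14)/730 = 0.02% per day up to −ln(1 − 0.36)/365 = 0.12% per day. With mean dwell 0.5 + 14 = 14.5 days, the upper value gives about 0.0012 × 14.5 × 300 ≈ 5 Yes lines. Day-7 patency would then be 1 − 5/300 = 0.983 if all five were dosed just after placement, and 1.000 if all five were dosed after day 7. The gap is about two points.

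**What the flag and dwell can still recover.** Suppose the Yes proportions are 4.9%, 13.9% and 25.9% at 5, 15 and 30 days. Then −ln(1 − 0.049)/5, −ln(1 − 0.139)/15 and −ln(1 − 0.259)/30 each return about 0.010 per day. Under a constant hazard, with removal unrelated to occlusion, the flag plus dwell identifies the hazard without dose times. This is current-status data: usable, but less precise than knowing the event times.

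**The case against.** The strongest reply is that nothing stated in the plan breaks. The endpoints are numbers of outcomes, timing of first loss of function is not among them, and no survival analysis is planned. A crude proportion and a dwell-day rate can both be calculated, and a current-status analysis can give patency at a stated time. For a line removed as 'occluded' with no Cathflo, the removal time approximates the loss of function. The extract is also not the only source: Methodology and Data Management provide for flow sheets and clinician notes, and the Appendix B form is only partly legible in the copy reviewed, so further fields there cannot be ruled out.

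All of that stands, and it limits the point. It does not remove it. The crude proportion depends on dwell. The total-dwell rate counts days after a first occlusion as at risk. The current-status estimate is less precise and needs removal to be independent of occlusion. None of the three recovers repeat episodes. Retrieving times by hand from notes, without a specified field, is a poor substitute for values that the query already reads.

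**Conclusion.** The point holds as a limitation of the extract that is cheap to remove. For lines treated and left in place, standard time-based patency, time to first Cathflo and repeat episodes cannot be obtained from the legible Appendix C items. The size depends on how common Cathflo use is, which the documents do not say: day-7 patency is undetermined over 0.64 to 0.84 at an assumed 36% share and about 14 days of dwell, but over only about two points at the hazard implied by the Background figure.

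Four stronger readings are tempting but unsupported.

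- A reader might infer that the patency rate cannot be derived at all, or that no analysis could give patency at a given day. The outcome is undefined, and the three cruder measures above are available.
- A reader might take the rise from 4.9% to 25.9% Yes between 5 and 30 days (5.3-fold at an assumed 1% per day) as the harm from missing dose times. It shows the effect of ignoring dwell, which is collected, and the assumed hazard is about eight times the upper value implied by the Background section (1%/0.12%).
- A reader might infer that dose times would show whether a lapse in care preceded an occlusion. That also needs dated lapses, and the legible Appendix C items carry no flushing, dressing or access dates.
- A reader might infer that the times are thrown away. The documents show only that the field does not return them.

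**What to change.** In Appendix C, return the date and time of each Cathflo administration during a line's dwell, one row per dose, and derive the Yes/No from those rows. The tool already asks for one row per medication, so this suits its format.

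Define catheter patency in the endpoint list as time from placement to the first Cathflo dose or to removal for 'occluded', whichever comes first. Report it at fixed days, by catheter type and adherence group. State in advance whether other removals are censored (Kaplan-Meier, which assumes that they are unrelated to occlusion) or treated as competing events (cumulative incidence). Add this to the Data Analysis section.

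The cost is one linked table and one added analysis. The times are already read to compute the flag, so no new source is needed.

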## Appendix C

**The following information will be acquired from Omnicell**

| Item  | Values/examples  | Description   |
|---|--|---|
| MRN   | 7 or 9 digit number  | Patient's MRN   |
| HAR   | 10 digit number  | Patient's HAR   |
| Completed administrations of Irritant/Vesicant Intravenous Medication | 
Name of IV Medication the patient was ordered:
 
 
• Acyclovir
 
• Amphotericin B
 
• Ampicillin sodium
 
• Ampicillin sodium/sulbactam sodium Partial parenteral nutrition
 
• Chemotherapeutic agents
 
• Ciprofloxacin
 
• Dextrose 10% or greater
 
• Dopamine
 
• Erythromycin
 
• Fluconazole
 
• Ganciclovir sodium
 
• High-concentration potassium chloride
 
• Iron dextran
 
• Mannitol
 
• Meperidine hydrochloride
 
• Morphine sulfate
 
• Nafcillin sodium
 
• Norepinephrine
 
• Oxacillin sodium
 
• Phenytoin sodium
 
• Promethazine hydrochloride
 
• Sodium bicarbonate
 
• Sodium nitroprusside
 
• Ticarcillin disodium
 
• Tobramycin sulfate
 
• Total parenteral nutrition (TPN)
 
• Vancomycin
 
 | A list of all irritant/vesicant medications that the patient was administered via intravenous route |

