#### Catheter Management and Care Documented: Appendix

Number and rate of times that the following best practice indicators were documented

- Department/Unit of catheter insertion
  - Operating Room
  - Bed-side
    - Cardiac Intensive Care Unit (CICU), Surgical Intensive Care Unit (SICU), Medical Intensive Care Unit (MICU)
  - Interventional Radiology
- Personnel performing the insertion
- Physician assistance Advance Practice Nurse

- Catheter insertion site
  - Subclavian
  - Internal jugular
  - Femoral
  - Cephalic vein
  - Basilic vein
  - Brachial vein
- Frequency of dressing changes
- Mask was used during dressing change procedure
- Mask was used during access procedure for CVCs, PICCs, HD catheters
- Accessing central line procedure
- Scrub the hub procedure document
- Alcohol impregnated cap
- CUROS cap
- Frequency of line flushing
- Flush with normal saline as per post infusion policy
- Flush with heparin lock as per post infusion policy
- Syringe size used for flushing documented
- Infusion pump high pressure alarm documented
- Type of products infused through line (medications, etc)

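### The Omnicell drug extract specifies no administration time and no line, so on its own it cannot show what was infused through a study catheter during its dwell

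*Combined protocol and SAP*

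**What the plan says.** Appendix C has two data requests. The second, to be filled from Omnicell, has three items: MRN, HAR and a medication item. The medication item is labelled "Completed administrations of Irritant/Vesicant Intravenous Medication". Its value is given as "Name of IV Medication the patient was ordered", followed by a list of drugs, and its description is "A list of all irritant/vesicant medications that the patient was administered via intravenous route". No other item appears in that table.

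The first request covers the lines themselves. The types to include are "CVC Double Lumen, CVC Single Lumen, Peripheral IV, PICC Double Lumen, PICC single lumen, PICC Triple Lumen". For each line it records "The date and time the LDAW was placed", the matching removal date and time, the removal reason and the duration in hours. It also derives a yes/no alteplase field, which is yes when the time of administration "falls within the timeframe that an LDAW was in place".

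In the body of the protocol, the list under Catheter Management and Care Documented, which follows the Primary Endpoints, includes "Type of products infused through line (medications, etc". The Catheter Insertion list names vesicant infusion as one documented reason for needing the catheter.

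**The concern.** The indicator concerns what went through a particular line, whereas the extract concerns what a patient received by vein. Anyone who joins the two on MRN and HAR will have a drug list beside each catheter and nothing to show that the two belong together.

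This matters because the protocol itself treats the infusate as a possible cause of its outcomes. Background and Significance attributes some occlusions to TPN precipitation and to low-pH drugs. TPN is on the Omnicell list, and catheter occlusion, thrombotic occlusion and drug precipitates are all listed complications. For a description of infusates by catheter to mean anything, the drug must have passed through that catheter. For it to bear on an occlusion, the drug must also have come first. The extract as specified can show neither.

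The wording adds a second problem. An order that was never carried out is not an exposure, and the row does not say which of the two it holds.

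**Working it through.** No arithmetic applies, because the question is whether the requested fields can support the use. Setting the fields side by side:

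| Field | Line request (Appendix C) | Alteplase field (Appendix C) | Omnicell request (Appendix C) |
|---|---|---|---|
| Patient keys | MRN, HAR | from the line request | MRN, HAR |
| Time | placement and removal, date and time | administration time matched to dwell | none specified |
| Line identity | line type | refers to any included line, not a named one | none specified |
| Given or ordered | not applicable | administered | both wordings in one row |

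**What one row can mean.** Take a patient with a PICC and a peripheral IV, and a row showing MRN, HAR and vancomycin, which is on the list. At least five histories produce that row:

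1. Given through the PICC during its dwell, before any occlusion.
2. Given through the PICC during its dwell, after an occlusion.
3. Given through the peripheral IV while the PICC was in.
4. Given before the PICC was placed or after it was removed.
5. Ordered but not given, if the value column is followed literally.

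Only the first is exposure of the study catheter ahead of an occlusion.

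**What each missing field would settle.**

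- Completion status, or a consistent use of administered, removes history 5.
- Administration time joined to placement and removal removes history 4. The placement and removal times are already requested.
- Administration time with a complication date separates history 1 from history 2. Appendix C has no complication date. It has a removal date and reason, so for a line removed because it was occluded it gives the removal time but not the onset.
- Line identity removes history 3. Time alone cannot, because the two lines were in at once. The same would hold for a second central line.

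**Two partial mitigations checked.** HAR may restrict the list to one hospital account. The documents do not define it, and an account key supplies neither a time nor a line. The sample layout headed "Please provide in this format" ends its columns with an ellipsis, which leaves room for more, but the Omnicell table names no further item.

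**The case against.** The strongest reply is that the Omnicell list need not be the source for the indicator at all. No passage names Omnicell as the source for products infused through the line. Methodology makes EPIC the primary source, including nursing notes and flow sheets, and Data Management adds review of clinician notes. The indicator list counts how often each item was documented, which is a chart-review task. Appendix B, the other part of the collection tool, is not legible enough in the text reviewed to rule out a field for infusates by line. All of this stands, and it limits the point to what this extract can support alone.

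It also rules out three stronger readings.

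- A reader might infer that every listed drug will be credited to the study catheter. The plan states no crediting rule. It leaves the linkage unspecified.
- A reader might infer that infusate exposure is lost to the study, as an indicator and as a confounder. Chart sources may supply it. Data Analysis plans summaries, Pearson correlation and unadjusted group tests, with no vesicant-by-occlusion contrast and no covariate adjustment, so no specified analysis is shown to be harmed.
- A reader might put a figure on the attenuation of a relative risk. The documents give no share of courses given elsewhere, no number of courses per patient and no expected effect. A share of misplaced courses is also not a share of false exposure flags. If half the courses missed the catheter (assumed), a patient with one course would be falsely flagged with probability 0.5. With three independent courses (assumed), the probability would be 0.5 × 0.5 × 0.5 = 0.125. A figure would reflect those assumptions and not this plan.

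The reply leaves the extract itself untouched. Run as written, it returns no time and no line, and its label and its value column disagree.

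**Conclusion.** The point holds as a defect in one data specification. The Omnicell request, taken alone, cannot place a listed drug in the study catheter, inside its dwell, or before rather than after a complication, and it does not say consistently whether the drug was given or ordered. The plan already sees the need for a time match, because it applies one to alteplase, but it does not extend that rule to this list.

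The size is small and cannot be expressed as a number from the documents. One exposure variable is affected; the comparison of adherent with non-adherent management is not shown to depend on it. The conclusion assumes that the Omnicell table is complete as printed. It does not assume that the extract is the study's only source on infusates.

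**What to change.** - Request one row per completed administration of each listed drug, with date and time, and join it to line placement and removal times as is done for alteplase.
- Where a complication date is abstracted from the chart, separate administrations before it from those after it. Appendix C does not supply that date.
- Take the line used from EPIC charting where it is recorded, and code line not charted as its own category rather than as unexposed.
- Make no line-level claim from the Omnicell list alone. Without line data, it can still be described as drugs given to the patient intravenously.
- Reconcile the item label, value and description, so that the row means administered or ordered but not both.

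The cost is an added time column and a join, settled before the extract is run. The line is the harder part: the documents do not say that Omnicell holds it, so it may need EPIC abstraction and may be incomplete.
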